6.5 Procedures

Following enrollment and completion of baseline surveys, participants will be randomized using a computer program developed by the study biostatistician to the BI or UC groups.

Behavioral Intervention: Participants that are randomized to the intervention group will be able to begin treatment sessions at different times points to accommodate new bariatric patients that complete surgery during the study duration. During the course of the study, there will be two 4-month bi-weekly session periods with at least two separate groups per session period. Therefore, there will be at least 4 time points that new patients can begin the process to complete all 8 individualized sessions. We estimate 10-15 patients per bi-weekly group for 60-minute sessions. The intervention will be structured such that each session will function independently (Table 2).

Table 2. Treatment Session Chart

First Round				
Month	Week	Session #	Group #	Milestone
March	Week 1	1	Group 1	First session initiation
	Week 2	1	Group 2	
	Week 3	2	Group 1	
	Week 4	2	Group 2	
April	Week 5	3	Group 1	
	Week 6	3	Group 2	
	Week 7	4	Group 1	
	Week 8	4	Group 2	
May	Week 9	5	Group 1	
	Week 10	5	Group 2	
	Week 11	6	Group 1	
	Week 12	6	Group 2	
June	Week 13	7	Group 1	
	Week 14	7	Group 2	
	Week 15	8	Group 1	
	Week 16	8	Group 2	First session surveys complete
Second Round				
July	Week 1 Session start delay due to July 4 th holiday.			
	Week 2	1	Group 1	Group 1 start
	Week 3	No group meeting		
	Week 4	2	Group 1	
August	Week 5	1	Group 2	Group 2 start
	Week 6	3	Group 1	
	Week 7	2	Group 2	
	Week 8	4	Group 1	
September	Week 9	3	Group 2	
	Week 10	5	Group 1	
	Week 11	4	Group 2	
	Week 12	6	Group 1	
October	Week 13	5	Group 2	
	Week 14	7	Group 1	
	Week 15	6	Group 2	
	Week 16	8	Group 1	Group 1 complete
	Week 17	7	Group 2	
November	Week 18	No group meeting		
	Week 19	8	Group 2	Group 2 complete

*A group three may be added to a session period to accommodate patient schedules if needed.

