The intervention will focus on addressing psychosocial changes after surgery, strategies for postoperative diet and adherence, and preventing weight regain (Table 3). Patients will collaboratively set goals for diet, physical activity, adherence and other behavioral changes tailored to the needs of each participant. Session content and intervention duration are evidence-based, derived from a meta-analysis of post-operative interventions aimed at using behavioral management strategies to enhance weight loss following bariatric surgery²⁰.

Confidentiality and group parameters and expectations will be introduced at the beginning of each session where new patients can start (treatment sessions 1&4 of first 4-mo bi-weekly session and treatment session 1 of second 4-mo bi-weekly session). Participants will be provided information regarding prevention of weight regain and resources for tracking and self-monitoring weight, diet and physical activity. Motivation for weight loss and participation in the group will also be discussed.

Sessions will contain a uniform structure to allow for easy transition of members in and out of the group. Sessions will start with an introduction of new members and review of participant progress on their goals and action plan or homework from the previous session. The majority of the session will be spent introducing and discussing new material and participants will be asked to develop a new action plan and state their goals at the end of the session. Make-up sessions will be offered for participants who miss a group.

Table 3. Intervention Content

Session	Primary Content
1	Preventing malnutrition (vitamins, protein intake, etc.)
2	Address problematic eating patterns after surgery (grazing, loss of control over eating, scheduling and emotional eating) Part 1
3	Address problematic eating patterns after surgery (grazing, loss of control over eating, scheduling and emotional eating) Part 2
4	Physical activity for health and wellness (w/side benefit of weight maintenance)
5	Managing special occasions: holidays, family gathering, restaurant eating, and vacations
6	Relationships and social support after bariatric surgery
7	Body Image
8	Taking stock and maintaining progress (relapse prevention)

The full Group Session Interventional Outline is attached.

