A member of the research team will remind the participants that randomize to the Intervention Group the day before each session either via phone or email (if participant chooses email communication they will provide the study team with their email address).

Should any participant express significant psychiatric distress in group, such as emotional reactions to weight loss or how relationships are affected, the group leader (a clinical psychology resident) will assess the participant immediately after group and consult with the study PIs ([name] or [name]). The group leader and study PI(s) will refer the participant for further treatment as appropriate. The group leader may also ask disruptive participants to leave group at any time.

Usual Care:

Participants randomized to usual care will complete surveys at postoperative clinic visits or if necessary, via mail. Upon study completion, patients randomized to usual care will be offered the 8 sessions provided to the BI group. This group will run after all study data have been collected.

Table 4. Compensation and Reimbursement

Behavioral Intervention Group	Compensation(Surveys) Reimbursement (Sessions)	Usual Care Group	Compensation (Surveys)
Baseline Surveys	\$50	Baseline Surveys	\$50
Session 1	\$15	N/A	N/A
Session 2	\$15	N/A	N/A
Session 3	\$15	N/A	N/A
Session 4	\$15	N/A	N/A
Session 5	\$15	N/A	N/A
Session 6	\$15	N/A	N/A
Session 7	\$15	N/A	N/A
Session 8	\$50	Final Surveys	\$50
TOTAL	\$205	TOTAL	\$100

Measures:

Surveys for Aims 1-2 will be administered to all participants at post op baseline (within two weeks of signing consent) and then at the completion of the 8 treatment session timeframe for both the BI and UC groups. Aim 3 measures of feasibility and satisfaction will be administered to BI participants only and at one time point, at study conclusion. Demographic, surgical and medical information will be collected from the EMR including weight (kg), height (cm), age at enrollment, sex, race/ethnicity, surgery type, insurance status, diagnoses and medication.

(Surveys are attached).

1. SF-36, Health-Related Quality of Life (HRQoL, primary outcome): As part of the Medical Outcomes Study (MOS), RAND developed the 36-Item Short Form Health Survey (SF-36). The SF-36 is a set of valid, reliable³⁴⁻³⁶, and easily administered QoL measures that have been used in obese populations^{37,38}.

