6.5.1 Study Time and Events Table

Study Month	1	2	3	4	5	6	7	8	9	10	11	12
IRB Completion												
Recruitment BI + UC, Baseline Measures (n=80)												
Intervention, BI group (n=20), group 1												
Intervention, BI group (n=20), group 2												
Data Analysis												
Manuscript and Grant Preparation												

Figure 6.5.2: Study Flow Diagram

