6.8.2 Statistical Power and Sample Size Considerations

Previous research⁵⁴ indicates that bariatric surgery patients report mean (SD) SF-36 subscale scores before and after surgery of:

	Preoperative	Postoperative	Effect Size
Role - Emotional	74.9 (34.4)	92.3 (22.1)	0.56 SD
Mental Health	70.5 (17.4)	74.6 (18.9)	0.2 SD
Mental Health Composite Score	48.9 (10.1)	52.1 (8.4)	0.3 SD

We aim for a difference of 2/3 standard deviation in scores between groups at 4 months postoperatively. A sample size of 40 participants per group will have 83% power to detect an effect size of 2/3 SD using a two group t-test with a 0.05 two-sided significance level. If the effect size is small than 2/3 SD, we will still be able to assess the level of confidence on the observed differences that will be used to design a large study. When the sample size in each group is 40, a two-sided 95.0% confidence interval for the difference of two means in mental health composite score will extend 4.4 from the observed difference in means, assuming that the common standard deviation is known to be 10.1 and the confidence interval is based on the large sample z statistic.

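### The 83% power and 4.4-point interval assume 40 independent, fully observed patients per arm, but the intervention is delivered in about four groups and no loss is allowed for

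*Combined protocol and SAP*

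**What the plan says.** Section 6.8.2 states: "A sample size of 40 participants per group will have 83% power to detect an effect size of 2/3 SD", using a two-sided 0.05 t-test. It adds a 95% interval half-width of 4.4 points for the mental health composite score, from 40 per group, a known SD of 10.1 and a z statistic. If the effect is smaller than 2/3 SD, the confidence around the observed difference is to inform a larger study. No ICC, design effect or loss rate appears.

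On delivery, section 6.5 says "there will be two 4-month bi-weekly session periods with at least two separate groups per session period" and "We estimate 10-15 patients per bi-weekly group for 60-minute sessions". The footnote to Table 2 adds: "A group three may be added to a session period to accommodate patient schedules if needed". Section 6.5.1 lists BI as two sets of 20, the first as "Intervention, BI group (n=20), group 1". UC has no sessions until all data are in: "Participants randomized to usual care will complete surveys at postoperative clinic visits or if necessary, via mail".

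Section 6.8.1 analyses continuous outcomes by independent t-tests, with ANCOVA for wave or baseline covariates only if needed. Missing data go to multiple imputation, with best- and worst-case analyses. Section 6.2.1 enrols about 80, and attrition is an endpoint in section 6.7.

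**The concern.** The assumptions behind the two figures do not match the design in two respects.

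- **Clustering.** BI participants share a group, its leader and its discussions; UC participants share nothing comparable. The design is partially nested. If outcomes correlate at all within a BI group, the independent t-test understates the standard error. A wave term does not repair this, because each wave holds at least two groups.
- **Loss.** Enrolment equals 2 × 40, and the figures need 40 observed per arm. Any missing month-4 outcome lowers power and precision. Loss at random does not affect type I error.

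At stake are the 5% level of the efficacy comparison and the interval to be passed to the next trial's design. An interval without group variance would pass on too little uncertainty.

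**Working it through.** **Inputs from the documents:** 40 per arm, d = 2/3, two-sided α = 0.05, SD 10.1 (6.8.2); at least 2 × 2 = 4 BI groups, so 40/4 = 10 per group (6.5). **Assumed:** ICC 0 to 0.10, loss 0 to 30%, and a baseline-to-final correlation r = 0.5.

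**1. The plan's own figures.** Noncentral t with 78 df and noncentrality (2/3)/√(2/40) = 2.98 gives power 83.8% (82.8% with 39 per arm). Half-width: 1.96 × 10.1 × √(2/40) = 4.43. Both figures reproduce. The expected t-based half-width is 4.48, and half-widths below are on that basis.

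**2. Effect of clustering on the planned t-test.** With total variance 1 in each arm, the BI mean has variance [1 + 9 × ICC]/40 and the UC mean 1/40. At ICC 0.05 the true SE is √(2.45/40) = 0.247, but the t-test works with √(2/40) = 0.224. The critical value 1.99 then acts as 1.99 × 0.224/0.247 = 1.80. That gives a type I error of 7.2% by a normal tail, or 7.6% by t with 78 df. Simulation (1,000,000 trials per cell, 4 × 10 BI against 40 UC):

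| ICC | Type I error | Coverage | Rejects at 2/3 SD | Half-width |
|---|---|---|---|---|
| 0 | 5.0% | 95.0% | 83.7% | 4.5 |
| 0.01 | 5.5% | 94.5% | 83.2% | 4.5 |
| 0.02 | 6.1% | 93.9% | 82.8% | 4.5 |
| 0.05 | 7.7% | 92.3% | 81.4% | 4.5 |
| 0.10 | 10.5% | 89.5% | 79.7% | 4.5 |

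The mean estimate stayed within 0.0004 SD of the truth in every cell. With six groups of 7, type I error at ICC 0.02, 0.05 and 0.10 is 5.7, 6.7 and 8.7%.

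**3. A group-adjusted analysis.** For balanced groups the SE is √[(MSG + MSR)/40]. MSG is the between-group mean square in BI (3 df). MSR is the residual mean square pooled over BI-within-group and UC (36 + 39 = 75 df). Satterthwaite df = (MSG + MSR)²/(MSG²/3 + MSR²/75). With the group variance not bounded at zero:

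| ICC | Type I error | Power, no loss | Half-width | Power, 20% loss | Half-width |
|---|---|---|---|---|---|
| 0 | 5.4% | 76.5% | 4.9 | 67.4% | 5.5 |
| 0.02 | 5.6% | 72.0% | 5.2 | 64.0% | 5.7 |
| 0.05 | 5.8% | 65.8% | 5.6 | 59.2% | 6.1 |
| 0.10 | 6.1% | 57.5% | 6.2 | 52.5% | 6.7 |

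The ICC 0 row shows the pure degrees-of-freedom cost: 83.8% to 76.5%, and 4.5 to 4.9. Median df is about 14 at ICC 0 and 8 at ICC 0.10. Bounding the variance at zero gives type I error of 3.5 to 5.0% and about 1 to 2 fewer power points.

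**4. Loss alone, under independence.** If imputation uses a baseline score correlating r with the final score, the variance of an arm mean is SD²[(1 − r²)/n_obs + r²/40]. At 20% loss and r = 0.5: 0.75/32 + 0.25/40 = 0.0297, so the effective n is 33.7.

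| Loss | Observed per arm | Power, nothing recovered | Half-width | Effective n, r = 0.5 | Power |
|---|---|---|---|---|---|
| 10% | 36 | 79.7% | 4.7 | 36.9 | 80.7% |
| 20% | 32 | 74.7% | 5.0 | 33.7 | 76.9% |
| 30% | 28 | 68.8% | 5.4 | 30.3 | 72.3% |

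**The case against.** - **The ICC is unknown, and clustering hardly moves the 83%.** Both are true. The planned test still rejects in about 80 to 83% of trials at 2/3 SD, and at ICC 0.01 the harm is negligible. The lower power figures belong to a model the plan does not use. What remains is the lost 5% level and an interval that is too narrow, material from about ICC 0.05.
- **Four groups is a minimum, and the groups are porous.** The plan says "Sessions will contain a uniform structure to allow for easy transition of members in and out of the group" and "Make-up sessions will be offered for participants who miss a group". More groups shrink the inflation, and blurred membership makes any cluster model approximate. Neither makes participants independent.
- **The remedy is expensive with so few groups.** As the primary analysis it loses about 7 power points at ICC 0, with little gain in type I error at ICC 0.02 or below. This is a sound reason not to insist that it replace the t-test. Kept as a sensitivity analysis, it leaves the primary test's inflation in place but makes it visible.
- **An interval built on a poorly estimated group variance is a weak input to the next trial.** The variance estimate is zero or negative in about 43% of trials at ICC 0.05. The small df carry part of that imprecision into the interval; the t-test carries none.
- **Imputation and ANCOVA offset loss.** Imputation recovers part. ANCOVA on the baseline score at r = 0.5 would give about 90, 86 and 81% power at 10, 20 and 30% loss under independence. But 6.8.1 makes that adjustment optional and does not name the baseline score.
- **The half-widths concern the composite, while 6.8.1 names the emotional scale as primary.** Correct; the plan itself uses the composite here. In SD units, 4.5 against 5.6 is 0.44 against 0.55, whichever scale is meant.
- **It is a pilot.** That softens the consequence for power. It strengthens the case for an honest interval, which is the stated fallback product.

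**Conclusion.** The concern holds and should be fixed. It is certain that 6.8.2 assumes independence and complete data, that BI is grouped, that no group term is planned and that loss has no allowance. The size is conditional on ICC and loss rates the documents do not give. With four fixed groups of 10, type I error runs from 5.5% at ICC 0.01 to 10.5% at ICC 0.10, behind an interval that stays near 4.5 points when a group-adjusted one would average 5.0 to 6.2. Loss of 10% is enough to bring power just under 80% if imputation recovers nothing, and to about 81% if it recovers what r = 0.5 allows. The treatment estimate is unbiased, and there is no arithmetic error.

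**What to change.** **In 6.8.2:** state that 83% and 4.4 hold under independence and complete data. Add a short table of power and half-width over ICC 0 to 0.10 and loss 0 to 30%, on one basis (z or t) throughout, with the degrees-of-freedom cost shown separately.

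**In 6.8.1:**
- Record, prospectively, the group to which each BI participant is first assigned.
- Prespecify a partially nested model: arm fixed, random intercept for BI group, each UC participant a singleton, Satterthwaite or Kenward-Roger df. Report it beside the t-test, at least as a sensitivity analysis, and carry its interval into the larger study's design. Whether it becomes primary is the trial statistician's choice.
- Fix in advance whether the group variance may go below zero.
- Note that later entry points, movement between groups and make-up sessions make the clusters approximate.
- Report the ICC as descriptive only.

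**Cost:** some wording, one recorded variable and a few lines of code; no extra patients. The price is a wider interval on few df and less favourable stated figures. If made primary, the model loses about 7 power points even at ICC 0 (about 10 if bounded); as a sensitivity analysis it costs no power.

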6.9 Data Management

6.9.1 Data Collection and Storage

An electronic database will be created and data will be entered into the database by research assistants. The database will be password protected and paper surveys kept in a locked file drawer. Each participant will be assigned a unique study ID number. A list of study ID numbers with associated identifying information (e.g., name, medical record number) will be electronically on a secure, password protected server. Access to the identifiers will be limited to study team members that require use of the identifiers.

6.9.2 Records Retention

Study records will be retained for 6 years. After 6 years, the study-specific database will be deleted and paper surveys shredded.

7 SAFETY MONITORING

This study will examine the effect of a psychological intervention in bariatric surgery patients compared to usual care controls. The proposed assessments are believed to pose minimal risk to participants. Group leaders will continually monitor for adverse events during the study duration, including worsening psychiatric distress and post-operative complications associated with bariatric surgery.

A subject's AEs and SAEs will be recorded and reported from the signing of the informed consent form until completion of study.

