4.1 Hypothesis

We hypothesize that BI patients will experience significant improvements in psychosocial functioning and better compliance compared to UC. As secondary outcomes, we will evaluate within group changes (BI group) from enrollment to completion of 4-month intervention program as well as outcomes in higher risk versus lower risk patients based on their initial preoperative psychosocial evaluations. We hypothesize that the BI group will display higher levels of dietary adherence and physical activity and attend more postoperative appointments, compared to UC.

4.2 Specific Aim 1

To assess the efficacy of a 4-month behavioral intervention (BI) program after bariatric surgery on psychosocial functioning compared to usual care (UC). Psychosocial outcomes assessed will be quality of life (primary), mood (depression/anxiety), eating behaviors, self-efficacy and interpersonal functioning using standardized measures.

4.3 Specific Aim 2

To evaluate the efficacy of a 4-month behavioral intervention program on postoperative dietary and lifestyle adherence compared to the UC.

4.4 Specific Aim 3

To assess the feasibility of a 4-month behavioral program in postoperative bariatric surgery patients. We will evaluate recruitment, attrition, safety and patient/provider satisfaction in the BI group.

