2. PHQ-9, Patient Health Questionnaire (depression): The PHQ-9 is a brief screening tool already integrated into GHS standard of care that screens for depression severity (sensitivity and specificity=88%). Scores of 5=mild depression, 10=moderate, and 15+=severe.
3. State-Trait Anxiety Inventory (STAI, anxiety): The STAI⁴⁰ is a 40-item assessment of anxiety symptoms and scored on a 4-point Likert scale. Internal consistency ranges from 0.86-0.95; test-retest reliability range 0.65-0.75 over a 2-month interval. It has demonstrated good construct and concurrent validity⁴⁰, and has been used in patients with obesity⁴¹.
4. Weight Efficacy Life-Style (WEL)⁴²: The Short form WEL is a 8-item measure that evaluates an individual's sense of self-efficacy in resisting the urge to eat in various situations. Internal consistency ranges from 0.70-0.90 and it has demonstrated sensitivity to change following weight loss interventions with obese populations.
5. The Paffenbarger Physical Activity Questionnaire (PPAQ)⁴³: The PPAQ is an 8-item, self-administered questionnaire designed to measure participation in leisure time. Respondents report the number of city blocks they walk and flights of stairs they climb on a typical day, as well as to list the frequency and duration of any sports or recreational activities they participated in over the past year. From these questions, a physical activity index (PAI) is computed, providing an estimate of energy expenditure. The PPAQ is used in bariatric surgery research⁴⁴.
6. Loss of Control Over Eating Scale-brief⁴⁵: The 7-item version of the LOCES is a brief measure of the experience of loss of control over eating over the past 28 days and is

[figure not shown]
scored on a 5-point Likert scale. The brief version of the full 24-item measure has demonstrated high internal consistency (0.93) and test-retest reliability ($r=0.82$) among non-clinical populations. The 7-item version is highly correlated with the 24-item version of the measure ($r=0.96$), which has also demonstrated good convergent and discriminant validity and was subjected to a more rigorous development and validation process than alternative measures.

7. Emotional Eating Scale (EES)⁴⁶. The EES is a 25-item scale that evaluates an individual's urge to eat while experiencing a range of emotions. The measure has demonstrated good discriminate validity, test-retest reliability, and sensitivity to change following treatment for weight loss and/or binge eating.

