6.8.1 Statistical Analysis Plan

Randomization will be conducted using randomization schema generated by the Biostatistician. Randomization to UC or BI will occur following consent. It is plausible that yellow light patients may experience greater benefit from the intervention. We will examine the comparability of demographics characteristics between two groups at baseline. If baseline demographic factors are not balanced between the two groups, we will then adjust for these factors during final analyses.

The primary outcomes will be the difference in mean HRQoL scores (emotional scale) as assessed by the SF-36 between the BI and UC groups at postoperative month 4 (assessment time frame will be postoperative month 1 to month 4). Continuous variables will be analyzed using independent t-tests. We will evaluate the appropriate assumptions using Shapiro–Wilk or Kolmogorov–Smirnov tests (normality) and a Brown–Forsythe test or a Q–Q plot (homogeneity of variance). Should the normality assumption be violated, we will then attempt transformations. If necessary, ANCOVA will be used to control for wave (1 vs 2) or other baseline covariates.

Secondary outcomes include differences between groups in the remaining HRQoL scales. Similar methods as described for the primary outcome will be used for the secondary outcomes. Additionally, within group analyses (secondary) will use paired t-tests. Categorical variables will be analyzed by chi-squared tests.

We will conduct intent-to-treat analysis to determine differences in primary and secondary outcomes using data from all randomized participants. Missing data will be handled using multiple imputation⁵⁵. We will also conduct sensitivity analyses such as best and worst case analyses⁵⁶.

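### Worsening psychiatric distress is a named harm, but the plan has no count of participants who worsen that is made the same way in both arms

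*Combined protocol and SAP*

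**What the plan says.** On the harm, section 7 has group leaders watch for adverse events throughout the study, "including worsening psychiatric distress and post-operative complications associated with bariatric surgery". It also states: "A subject's AEs and SAEs will be recorded and reported from the signing of the informed consent form until completion of study". Section 7.1 has all events notified to the IRB and serious ones followed until they resolve or stabilise. Sections 6.5 and 8.2 describe what happens when a participant expresses marked distress during a group.

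On safety as an outcome, section 4.4 (Specific Aim 3) says: "We will evaluate recruitment, attrition, safety and patient/provider satisfaction in the BI group".

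On measurement, section 6.5 gives the Aim 1 and 2 surveys to all participants in both arms, at post-operative baseline and at the end of the eight-session period. These include the PHQ-9 (depression) and the STAI (anxiety). For the PHQ-9 the protocol prints severity bands: "Scores of 5=mild depression, 10=moderate, and 15+=severe". Section 4.2 places mood among the efficacy outcomes.

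On analysis, section 6.8.1 says: "Continuous variables will be analyzed using independent t-tests". ANCOVA is available if needed, secondary outcomes are handled similarly, and within-group change is tested by paired t-test. Chi-squared tests are reserved for categorical variables, but no categorical PHQ-9 or STAI variable is defined.

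**The concern.** The protocol foresees a specific harm and promises to evaluate safety, but no planned output compares that harm between arms at the level of the individual.

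Leader observation covers one arm. UC participants attend no groups until all study data are in; they return surveys at clinic visits or by mail. Leader-detected distress is therefore unequal between arms by design.

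The surveys are collected alike in both arms, but they enter the analysis as means. A mean can favour BI while a minority of that arm deteriorates.

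Section 4 says the data will support applications for larger trials. A safety statement resting on one-arm observation plus a mean mood score would be thin support for them.

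**Working it through.** **1. The plan's own figures.** With 40 per group, a 2/3 SD effect and two-sided 0.05, the noncentral t with 78 df gives 83.8% power (normal approximation 84.6%), against the stated 83%. The stated CI half-width of 4.4 is 1.96 x 10.1 x sqrt(2/40) = 4.43. Both reproduce. Both concern means; the plan states no figure for deterioration.

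**2. What each planned output can show about worsening.**

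- Independent t-test or ANCOVA: difference in means between arms.
- Paired t-test: mean change within an arm.
- Chi-squared: proportions, but no worsening variable is defined for it to use.
- Best- and worst-case analyses (6.8.1): introduced as sensitivity analyses after the missing-data sentence; they define no count of deterioration.
- Analysis by light status (section 5): a subgroup comparison.
- Adverse event records: individual cases, but no analysis or between-arm comparison is specified.

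None yields a count of participants who worsened, by arm, from the same instrument.

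**3. Can a mean hide a minority?** The documents give no PHQ-9 SD, deterioration threshold or deterioration rate, so these inputs are assumed. Let a fraction f of BI worsen by 5 points (the spacing of the printed bands), let the rest improve by g, and let UC improve by u on average. With equal baselines, the expected BI minus UC difference is

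5f - (1 - f)g + u, where negative favours BI.

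With g = 4 and u = 0:

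- f = 0.10 (4 of 40): 0.50 - 3.60 = -3.10
- f = 0.15 (6 of 40): 0.75 - 3.40 = -2.65
- f = 0.20 (8 of 40): 1.00 - 3.20 = -2.20

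For an assumed SD of 4 to 6, -3.10 is 0.78 to 0.52 SD and -2.20 is 0.55 to 0.37 SD. With g = 2 the three differences shrink to -1.30, -0.95 and -0.60. The result also depends on u: with g = 4 the sign reverses once UC improves by more than 3.10, 2.65 or 2.20 points respectively. Masking is therefore possible under some assumptions and absent under others.

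**4. What could a count by arm show at 40 per arm?** Take 6/40 v 2/40 as an example. The Wilson 95% limits are 0.071 to 0.291 and 0.014 to 0.165. The Newcombe interval for the difference of 0.10 is

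- lower: 0.10 - sqrt((0.150 - 0.071)^2 + (0.165 - 0.050)^2) = -0.04
- upper: 0.10 + sqrt((0.291 - 0.150)^2 + (0.050 - 0.014)^2) = 0.25

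For true rates of 5% v 15%, exact power is 35% (chi-squared) or 18% (Fisher), and 80% power needs 141 per arm. For 5% v 20% it is 57% or 41%, and 76 per arm are needed. The count is useful as description, not as a test.

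**The case against.** The strongest reply is that individual harm is already covered. Events are recorded for every subject from consent to completion and notified to the IRB, serious ones are followed up, and distress expressed in group is assessed at once. The PHQ-9 is also part of routine care at the site, and diagnoses and medication come from the EMR. This stands as far as it goes: individual cases are not invisible, and it would be wrong to infer that safety rests solely on what a leader notices. It does not supply a comparison, because the only named monitors see one arm and no analysis of events is planned.

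A second reply is that the PHQ-9 measures depression and is never designated as the measure of this harm. That is fair; the link is an inference. A reader might also take the PHQ-9 to be the only relevant instrument. It is not: the STAI, SAS-SR and SF-36 are given to everyone at both times. This is why the remedy should include the STAI.

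A third reply concerns size. It is tempting to argue from the BI arm alone: 36 of 40 improve by 2 points and 4 worsen by 10 (say from 6 to 16), so the mean change is (-72 + 40)/40 = -0.8 and the plan reports improvement while 10% become severe. That example does not work. It has no UC arm; if UC also improved by 2, BI would be -0.8 + 2 = 1.2 points worse, and the mean would point towards harm. Nor would the paired test declare improvement: SD = sqrt((36 x 1.2^2 + 4 x 10.8^2)/39) = 3.65, t = -0.8/(3.65/sqrt(40)) = -1.39, p = 0.17.

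Finally, a move to a worse band can be a single point (9 to 10), while a rise from 5 to 9 is missed. This is correct, and it is a reason to add a point-change count beside the band shift.

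**Conclusion.** The point holds as a gap in the safety analysis. The plan names a harm and collects before-and-after symptom scores alike in both arms, but specifies no individual-level count of worsening by arm. The adverse event route cannot fill this gap because its named monitors see BI participants only.

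A reader might go further and infer that the planned analysis will conceal harm, or that participants are likely to deteriorate. The documents support neither. Masking is arithmetically possible under the assumed changes shown above and depends heavily on how UC changes. No PHQ-9 SD, threshold or rate is given from which to judge its likelihood.

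The primary endpoint, sample size and primary analysis are untouched. The change is worth making because it is cheap and lets a pilot that promises a safety evaluation compare a harm it names.

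**What to change.** Add to section 6.8.1 a descriptive safety table by arm, containing:

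- the baseline-to-final PHQ-9 shift across the protocol's bands (<5, 5-9, 10-14, 15+);
- the number and percentage newly at 15 or above;
- the number and percentage worsening by a pre-specified point change, for example 5 points (the band spacing), so that one-point band crossings are not over-read;
- the between-arm risk difference for these counts with a 95% CI;
- participants without a final form, as a separate category;
- individual worsening on the STAI, summarised the same way with its own pre-specified change.

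State that the table is descriptive and carries no hypothesis test, and cite it in the Aim 3 safety conclusion. These are reporting thresholds only; they set no rule for referral or treatment.

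The cost is one more table from data already collected, with SAP wording only and no new visit or instrument. The drawback is wide intervals at 40 per arm, so the table cannot settle whether the programme causes worsening.
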